Inclusion criteria will include documented AF that has been treated in the last 30 days resulting in the restoration of normal sinus rhythm. The operational definition of AF for this study will include the presence of AF captured by the AliveCor® Mobile ECG, a standard 12 lead ECG, Holter, or any other external recording mechanism that documents AF. Over a six-month period, those individuals with \leq 7 days of AF will be considered paroxysmal, and those with greater than 7 days of continuous AF will be defined as persistent AF per the AHA/ACC/HRS guidelines. The main exclusion criteria for participants include documented permanent (chronic) AF, unwillingness to use technology and have one's clinical data collected over the study period, unwillingness to receive and read cardiovascular text messaging three times a week, and patients who have a documented medical history of cognitive impairment.

Data and Safety Monitoring

The study was approved by the Columbia University Medical Center Institutional Review Board. Participants provide written informed consent prior to enrollment and all data collection procedures are in accordance with the Health Information Portability and Accountability Act regulations.

Sample Size

A total of 300 participants with documented AF who are undergoing clinical treatment of their AF with electrical cardioversion, radiofrequency ablation and/or medical management to restore normal sinus rhythm will be enrolled. After a normal rhythm is restored, participants will be randomized to usual cardiac care (n= 150) or usual cardiac care plus the iHEART intervention (n= 150). The population will be recruited from the Columbia University Medical Center (CUMC) cardiac services and will include English and Spanish speaking participants.

Randomization

The randomization process will be performed by a random computer number generator in a one-to-one block allocation ratio. In order to achieve a balance of applicable participant characteristics in both the intervention and control groups, participants will be stratified based on age and gender.

Outcome assessments

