Study Intervention

Participants randomized to the iHEART intervention will receive an iPhone® and cellular service plan with unlimited data/text messaging, the AliveCor® Mobile ECG, and Behavioral Altering Motivational (BAM) text messaging three times a week for six months. BAM is an in-house database that automatically sends one-way text messages to the intervention participant related to their AF, as well as two underlying cardiovascular risk factors of their choosing.

AliveCor™ Heart Monitor

The AliveCor® Mobile ECG, an FDA-approved smartphone technology, works through a free application, "Kardia." It captures a highly sensitive (98%), specific (97%), and accurate (97%) single-lead ECG recording through two electrodes on the back of the smartphone[7]. When the application is opened, recording begins automatically when both electrodes make contact with skin (Figure 2). Transmissions are automatically uploaded to the study portal within the

AliveCor® “cloud”. All participants will receive in-person training on the use of the study equipment at enrollment. A return demonstration from the participant to the research coordinator will be required at baseline enrollment. This will include how to capture an ECG daily and in the setting of symptoms, as well as how to record any associated symptoms in the application.

All ECG images and any associated symptoms will be sent via WiFi or cellular network transmission to the AliveCor® cloud. A login will occur daily to the password-protected study database that will be stored on the AliveCor® cloud in order to review and interpret all ECG strips transmitted during the previous 24 hours. Any clinically significant arrhythmias, including AF or other arrhythmias, detected during the daily review of ECGs over the 6-month period will be immediately sent to the provider caring for the participant. The study team will ensure the provider has received the transmission, is aware of any ECG abnormalities, and will then be responsible for communicating such findings.

Smartphone

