The primary endpoint is detection of recurrence of AF. Secondary endpoints include treatment changes as a result of early detection of AF recurrence, study questionnaire scores at baseline and six months, including QoL, QALYs, and improvement in cardiovascular measures (e.g., blood pressure, glucose levels) and AF knowledge from baseline to 6 months. Outcome assessors will be blinded to group allocation.

Statistical Analysis

We will define and calculate recurrent AF detection rate as the ratio of the number of recurrent AF episodes to the number of person-months of follow-ups. We will compare the difference in recurrent AF detection rate over the six-month study period between the control group and the iHEART intervention group. Analysis of the potential moderating effects of demographic factors (e.g., age, gender, etc.) as well as the difference between the groups will be performed using multivariate Poisson regression.

We will compare the time-to-treatment between the iHEART intervention group and the control group with the application of survival analysis methods. For those who are treated for recurrent AF, the time-to-treatment is the time from beginning of study to the time of treatment. Those who are not treated for recurrent AF will be censored at the end of the sixth month, or the time of death should a subject die before the sixth month. We will apply the Cox proportional hazard model to examine and test the difference in the time-to-treatment between the intervention group and control group, with the adjustment for other potential confounders (e.g., age, gender). QALYs are calculated as follows: for each month of life lived at an EQ-5D index of x , the QALYs will be $x/12=0.0833x$ years. We will calculate QALYs during the 6-month study period for all participants by summarizing QALYs from baseline through sixth month. We will compare QALYs between the iHEART intervention group and the control group using a two-tailed independent sample t-test. To adjust for potential confounders (e.g., age, gender), multivariate linear regression models will be used. Additionally, we will compare change of quality of life (QoL) and symptoms of AF scores (AFEQT, AFKS, EQ5D and CCS-SAF scales, etc.) from baseline to 6 months between the two groups and between those with and without AF using linear mixed models (growth model).

Figure 1. Flowchart for Study Procedures

[figure not shown]

Table 1. Inclusion and Exclusion Criteria

Inclusion Criteria

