- Males and females (English or Spanish speaking) age ≥ 18 years with a prior history of AF in the last 30 days that was treated and normal rhythm restored
- Already utilizes a smartphone prior to enrollment
- Ability to successfully use the AliveCor™ Heart Monitor, capture a baseline ECG, and transmit on the day of enrollment
- Demonstrated ability to receive and read text messages on the day of enrollment
- Willingness to complete the study questionnaires at baseline and 6 months

Exclusion Criteria

- Documented permanent (chronic) AF
- Unwillingness to have their clinical data collected over the study period
- Unwillingness to receive and read cardiovascular text messaging three times a week.

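### The primary comparison of AF episode rates uses Poisson regression with no stated allowance for a variance that differs from the mean

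*Combined protocol and SAP*

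**What the plan says.** Under Study end-points: "The primary endpoint is detection of recurrence of AF". Statistical Analysis turns this into a rate, defining the "recurrent AF detection rate as the ratio of the number of recurrent AF episodes to the number of person-months of follow-ups". The numerator is episodes, not participants with a recurrence, so one person can count more than once. The same paragraph says that moderation by demographic factors "as well as the difference between the groups will be performed using multivariate Poisson regression".

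Nothing else is said about the variance of these counts. The document names no robust or sandwich standard error, scale parameter, negative binomial model, participant effect, dispersion check or fallback. The linear mixed models in that section are for questionnaire scores only.

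Three other places bear on how the counts will vary:

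- **Mixed population.** Under Sample Size, participants enter after "electrical cardioversion, radiofrequency ablation and/or medical management to restore normal sinus rhythm". Study Population separates paroxysmal AF from persistent AF: "those with greater than 7 days of continuous AF will be defined as persistent AF".
- **Intensive detection in the intervention arm.** Under AliveCor Heart Monitor, participants are taught "how to capture an ECG daily and in the setting of symptoms".
- **Less regular detection in usual care.** Under Outcome assessments, AF is found at routine visits, by pulse checks and by testing prompted by symptoms.

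**The concern.** A Poisson model takes its standard errors from the assumption that, given the covariates, the variance of a participant's count equals its mean. Two features of this trial strain that assumption in opposite directions.

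- **Differences in underlying rate.** Prior treatment and AF pattern differ between participants, while the covariates given as examples are demographic. Rate differences left after adjustment make the variance exceed the mean. Poisson standard errors are then too small and the result looks more certain than it is.
- **Long episodes.** A participant who is in AF cannot start a new episode. If rates are similar and episodes long, the variance falls below the mean. Poisson standard errors are then too large and the test is too cautious.

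At stake are the p-value and confidence interval of the primary comparison, and the moderation tests that use the same model. The estimated rate ratio is not in question. Finding recurrence in more participants is what the device is meant to do, and is no part of this criticism.

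**Working it through.** **Inputs from the plan.** 150 per arm, 6 months of follow-up (taken as 180 days), episodes per person-month, Poisson regression. The plan gives no episode rate, dispersion, significance level for this test or basis for N = 300, so it has no figure to reproduce. A two-sided 5% level and every rate, duration, spread and detection schedule below are assumptions.

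**Step 1. Closed form.** If the variance is φ times the mean in both arms, the Poisson standard error is wrong by a factor √φ, and the true size of a nominal 5% test is 2 × (1 − Φ(1.96/√φ)):

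| φ | True size |
|---|---|
| 0.68 | 1.7% |
| 0.78 | 2.7% |
| 1 | 5.0% |
| 1.5 | 11.0% |
| 2 | 16.6% |
| 3 | 25.8% |

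Simulation with chosen φ and means of 0.5 to 2 episodes agrees: 10.5–10.9% at 1.5, 16.3–16.5% at 2 and 25.6–26.0% at 3. The sandwich variance gave 4.9–6.0%, the highest value being at mean 0.5 and φ = 3.

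**Step 2. Ratios that follow from duration and rate differences, counting every onset in both arms.** One onset is expected per 180 days in sinus rhythm. Episode durations are exponential, and participants' rates have coefficient of variation (CV) 0, 0.5 or 1. Each cell shows φ, then the Poisson type I error from 20,000 simulated trials:

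| Rate CV | 3 days | 10 days | 30 days | 60 days |
|---|---|---|---|---|
| 0 | 0.97; 4.5% | 0.91; 3.7% | 0.78; 2.6% | 0.68; 1.6% |
| 0.5 | 1.20; 7.1% | 1.10; 5.9% | 0.92; 3.9% | 0.78; 2.6% |
| 1 | 1.85; 14.9% | 1.61; 12.0% | 1.25; 8.1% | 1.03; 5.1% |

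The sandwich error is 4.8–5.4% in all 12 cells. Negative binomial regression gives 4.7–5.7% in the six overdispersed cells but 2.1–4.3% in the six underdispersed ones, because it cannot represent φ below 1.

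**Step 3. Detected counts.** The endpoint is detected recurrence, so Step 2 fits only if detection is almost complete in both arms. Missed episodes thin the counts, which moves an overdispersed φ towards 1. With a recording every 30 days and CV 1, φ at 3, 10, 30 and 60 days becomes 1.06, 1.13, 1.06 and 0.93, against 1.85, 1.61, 1.25 and 1.03 for all onsets.

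Now let one arm detect daily and the other every 30 days. With means m₁, m₀ and ratios φ₁, φ₀ of the detected counts:

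- Poisson variance of the log rate ratio: (1/150)(1/m₁ + 1/m₀)
- correct variance: (1/150)(φ₁/m₁ + φ₀/m₀)
- standard error ratio: r = √[(φ₁/m₁ + φ₀/m₀)/(1/m₁ + 1/m₀)]
- non-coverage of a nominal 95% interval: 2 × (1 − Φ(1.96/r))

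The arm with fewer detected episodes dominates both variances. Across the 12 cells r runs from about 0.83 to 1.12, and non-coverage from about 1.7% to 7.9%. As a check, 1.96/0.83 = 2.36 gives 1.8%, and 1.96/1.12 = 1.75 gives 8.0%; the small differences come from rounding r. This step concerns coverage and not type I error, because the two schedules produce a real difference in detection rate.

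**Step 4. When both arms detect alike.** If both detect as 30-day recording would, closed-form type I error over the 12 cells is 1.8% to 6.6%. If both detect daily, it reaches 13.4% and 11.9% at CV 1 with durations of 3 and 10 days.

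**The case against.** The strongest reply is that this is an unspecified detail with little practical effect. The choice of standard error is an implementation matter within the named model, and the wording does not exclude a robust one. The endpoint is detected AF, and Outcome assessments does not describe near-complete detection in usual care, so the 12–15% errors of Step 2 do not describe this trial as designed. In the daily-versus-30-day scenario at CV 1, the expected z statistics with Poisson and correct variance are 7.7 and 7.3, 6.3 and 5.6, 3.0 and 2.8, and 1.6 and 1.6. Only one of the 12 cells crosses 1.96 (equal rates, 60 days, from 1.7 to 2.1), and there plain Poisson is the cautious choice.

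Much of this stands. It lowers the size and removes any claim about direction. It does not remove the gap, for two reasons. The 30-day schedule is itself an assumption, and usual-care testing depends on visits and symptoms. If that testing is uneven between participants, it could add dispersion that a fixed schedule does not show. Second, a variance method for the primary test that is left open can be chosen after the results are known.

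A reader might also infer that daily strips will be counted as separate episodes, since staff will "review and interpret all ECG strips transmitted during the previous 24 hours". The documents do not say so. The rate is defined on episodes, Study Population recognises continuous AF, and Table 1 requires a "prior history of AF in the last 30 days that was treated and normal rhythm restored", which suggests that a recurrence follows restored rhythm. What is missing is a written counting rule, and that is a separate clarification.

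**Conclusion.** The concern holds as a gap in the primary analysis: a count that can exceed one per participant is compared by Poisson regression with no stated protection if the variance differs from the mean. The omission is certain, but its size and direction are not. On detected counts, with the assumed rates, durations, spreads and schedules, the correct standard error is about 0.83 to 1.12 times the Poisson one, and a nominal 95% interval misses about 1.7% to 7.9% of the time.

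A reader might infer that the primary test has a seriously inflated false-positive rate. The documents do not support that. Errors of 12–15% arise only with near-complete detection in both arms and strong rate differences, and errors of 16–26% only at chosen ratios of 2 to 3, above the largest ratio (1.85) that the duration scenarios produce. In half of the Step 2 cells the Poisson test is too cautious.

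Two limits apply to the illustration. No covariates were simulated, so the CV stands for rate differences left after adjustment. The sandwich error rates come from all-onset counts and from chosen means of 0.5 or more, not from the sparser detected counts of Step 3.

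**What to change.** In Statistical Analysis, keep the episode rate and the Poisson model, state log person-months as the offset, and base the primary test and interval on a participant-level robust (sandwich) variance. This protects in both directions. Negative binomial regression is an alternative only if counts prove overdispersed.

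**Cost.** A change of SAP wording and no new data. The interval widens if counts are overdispersed: by √1.5 = 1.22, √2 = 1.41 or √3 = 1.73 at common ratios of 1.5, 2 or 3, but by at most about 1.12 in the detected-count illustration. It narrows if they are underdispersed. The effect on planned power cannot be computed, because no basis for N = 300 is given.

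**Optional clarifications, not part of the main point:**

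- Write one episode-counting rule for both arms, so that successive AF strips from one continuous recurrence are not entered as several episodes. A robust variance does not replace this rule.
- Report first documented recurrence as a supporting analysis from data already collected. It does not depend on how repeat AF is split into episodes, but it still depends on recording frequency. In the equal-rate scenario at 3, 10 and 30 days, daily recording detects a recurrence in 57%, 61% and 62% of participants, and 30-day recording in 9%, 27% and 46%.

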Upon study entry, all relevant clinical data will be collected at baseline and monthly throughout six months via an electronic medical records system review. This will be used to capture and quantify cardiac outcomes in both groups. In addition, all outside medical records will be requested, and participants will be contacted monthly to capture any hospitalizations, cardiac events, or changes in therapy that may occur outside of our center and clinics. AF in the usual care group may be detected during routine follow-ups with providers, as well as during self-evaluations such as a pulse check initiated as a result of participant-reported symptoms or changes in health status. AF may also be captured by a 12-lead ECG, pulse check, or heart sound auscultation during an exam that reveals an irregular heart rhythm. Participants in the usual care group may seek medical evaluation by their providers because of a change in their health status or symptoms (shortness of breath, palpitations, fatigue), which may lead to further cardiac monitoring or testing (e.g., echocardiogram) that may reveal AF. This could include Holter monitoring (24 hour) or extended cardiac monitoring (7-30 days) that may document AF and be the basis for changes in treatments prescribed by their providers (e.g., medication changes or dosage adjustments, cardioversion). In the intervention group, AliveCor® Mobile ECG transmissions will be read daily to detect recurrence of AF or other arrhythmias. All results and any treatment changes due to mobile ECG findings will be recorded over the course of the study period.

All study participants will be asked to complete a series of questionnaires including the Atrial Fibrillation Knowledge Scale (AFKS), the Canadian Cardiovascular Society Severity in Atrial Fibrillation scale (CCS-SAF), the Atrial Fibrillation Effect on Quality of Life (AFEQT), the Control Attitudes Scale-Revised (CAS-R), the Morisky 4-item Self-Report Measure of Medication-Taking Behavior (MMAS-4), the Self-Efficacy for Appropriate Medication Use Scale (SEAMS), the Short Form Health Survey (SF-36 Quality of Life), European Questionnaire 5 Dimensions (EQ-5D), the Patient Health Questionnaire (PHQ-9), and the State Trait Anxiety Inventory (STAI). These measures will be administered to both the intervention and control groups at baseline prior to any procedures, such as a cardioversion or ablation, and again at the 6-month follow-up visit for the purpose of comparison.

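### The primary analysis counts undefined AF episodes rather than first detected recurrence, so the rate comparison does not isolate detection

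*Combined protocol and SAP*

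**What the plan says.** The Study end-points section states: "The primary endpoint is detection of recurrence of AF". Read plainly, that is an event a participant either has or does not have.

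The Statistical Analysis section measures something else. It takes the "recurrent AF detection rate as the ratio of the number of recurrent AF episodes to the number of person-months of follow-ups", a count that can rise repeatedly in one participant. The group comparison, with possible moderators, "will be performed using multivariate Poisson regression". The effect measure is therefore by implication a rate ratio, although the text speaks of a difference in rates.

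The only duration rule is in Study Population, where "those with greater than 7 days of continuous AF will be defined as persistent AF". It separates paroxysmal from persistent AF. It does not say when one episode ends and the next begins.

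Ascertainment differs by design. iHEART participants are trained in "how to capture an ECG daily and in the setting of symptoms" (AliveCor Heart Monitor section), and their "AliveCor® Mobile ECG transmissions will be read daily to detect recurrence of AF or other arrhythmias" (Outcome assessments). By contrast, "AF in the usual care group may be detected during routine follow-ups with providers", or after symptoms, or by Holter or extended monitoring if a provider orders it. Clinically significant findings on the strips go to the treating provider at once, and treatment change after early detection is a secondary endpoint.

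**The concern.** Three features combine.

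- **Splitting.** Without an episode rule, AF that continues over several days can be scored once or several times. This matters mainly in the arm with daily strips. A single clinic ECG leaves little to split.
- **Feedback.** Counting does not stop at first detection or at treatment. A participant returned to sinus rhythm is at risk again and can add further episodes. If treatment prevents later AF, the count falls.
- **Mismatch.** The count thus combines whether recurrence was found, how continuing AF was divided, and what happened after it was found. The endpoint as worded asks only the first.

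Two analysts following the section faithfully could report different primary results from the same recordings, and the rule could be settled after the data are seen. A better variance for the Poisson model would not help, because it is the quantity being estimated that is unsettled.

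**Working it through.** The plan states no recurrence rate, AF duration, adherence or treatment effect, and no power calculation behind its 300 participants. There is no figure of its own to reproduce, and all rates below are assumptions.

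**1. One stretch of AF under different rules.** Take 10 days of continuous AF with daily strips, the day-5 strip missed, and one clinic ECG in usual care.

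| Counting rule | iHEART | Usual care |
|---|---|---|
| Each positive strip | 9 | 1 |
| Each run of consecutive positive days | 2 | 1 |
| Merge positives no more than 7 days apart | 1 | 1 |
| Participant with any detection | 1 | 1 |

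The plan selects none of the first three. The last needs no rule.

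**2. First model, same underlying AF in both arms.** Assumptions: recurrence hazard 1/120 per day over 180 days; half of participants in AF until treated, half with short paroxysms; daily strips against one usual-care check per 60 days on average; treatment 14 days after detection.

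Analytic check of the any-detection figures:
- iHEART, every recurrence seen: 1 − exp(−180/120) = 0.777.
- Usual care, persistent half (time to recurrence plus time to a check is under 180 days): 1 − 2·exp(−1.5) + exp(−3) = 1 − 0.446 + 0.050 = 0.604. If all AF were persistent, the ratio would be 0.777/0.604 = 1.29.
- Simulated usual care overall is 33%, which implies about 2 × 33 − 60 = 6% in the paroxysmal half.

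Simulated ratios, iHEART to usual care (person-months cancel when follow-up is equal, at 150 × 6 = 900 per arm):

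| Measure | Later AF unchanged by treatment | Later AF cut by 75% |
|---|---|---|
| Any detection (77–78% vs 33%) | about 2.3 | about 2.3 |
| Each AF spell counted once | about 3.5 | about 2.4–2.7 |

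The 2.4–2.7 range comes from two separate runs. With all AF persistent, the ratios are 1.3 for any detection and 1.8 for spells. Counting every positive strip would give about 23 (21 if all AF is persistent), but the plan does not say to count strips.

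**3. Second model, different assumptions.** AF onset 0.3 per month, varying between patients; 30% of episodes long (mean 30 days), the rest mean 2 days; strip adherence 0.9; device sensitivity 0.98 (the plan's figure); usual-care checks 0.33 per month, plus 40% of episodes prompting a check; treatment ends detected AF in about 7 days.

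| Later onset multiplied by | Each true episode once | Any detection | True onset-rate ratio |
|---|---|---|---|
| 1 | 4.13 | 2.11 | 1.03 |
| 0.5 | 3.19 | 2.13 | 0.83 |
| 0.2 | 2.65 | 2.18 | 0.68 |
| 0 | 2.23 | 2.23 | 0.56 |

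The episode ratio nearly halves as treatment works better, and the patient-level ratio hardly moves. With later onset unchanged, the rule alone gives 3.69 (7-day merge), 4.13 (true episodes) or 4.64 (consecutive-day runs).

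**4. Almost no patient-level gain.** With all AF long-lasting and always prompting a check, 63.5% against 62.1% of participants are detected (ratio 1.02). The rate ratio is 1.01 with a 7-day merge, 1.13 by true episode and 1.51 by consecutive-day runs.

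**The case against.** The strongest reply is that more frequent looking is the intervention. Aim 1 in Study Design compares mobile ECG with usual care for both detection and treatment of recurrent AF, so unequal sampling is the intended contrast, and repeat recurrences are a legitimate target that a first-event analysis sets aside. This stands. Unequal sampling is not the defect, first detection also depends on it, and repeat recurrences belong in the report.

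A reader might go further and infer that the rate does not measure detection at all, that effective treatment could make the device look the worse detector, or that the effect would be inflated some twentyfold. The documents do not support these readings. Every simulated detection or episode ratio was at or above 1. A strong treatment effect moved the spell ratio down towards the any-detection ratio, not below 1. The ratios above 20 require counting strips, whereas the plan says episodes.

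The simulations also have limits. The first lets daily strips catch every recurrence and gives usual care no symptom-driven detection, although Outcome assessments describes routine visits, symptom-prompted evaluation, optional 24-hour Holter or 7–30 day monitors, and monthly record review and contact. The second model allows for missed strips and symptom-prompted checks and shows the same dependence on rule and treatment.

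**Conclusion.** The point holds in this form: the planned rate comparison does not isolate detection, because the episode is undefined and counting continues through treatment prompted by detection. It affects the primary analysis and should be corrected before that analysis is run.

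The size is illustrative. In the first model, 2.3 for any detection stands against about 3.5 for spells, or 2.4–2.7 with a 75% cut in later AF. The second model gives 2.1–2.2 against 2.2–4.1 when each true episode counts once. These values rest on assumed rates, durations, adherence and treatment effects. That the result depends on the counting rule and on later treatment follows from the definition itself and does not rest on those values. Nothing here shows that the direction of the comparison would reverse.

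**What to change.** - **Primary measure.** Use time from randomisation to first documented AF recurrence, one event per participant. Compare arms with the Cox model already planned for time-to-treatment, and also report the 6-month proportion with any detected recurrence. This matches the endpoint wording, needs no merging rule, and cannot be altered by treatment given after that first detection.
- **Documentation standard.** Study Population defines AF by an external recording that documents it, whereas Outcome assessments lists pulse check and auscultation among the ways AF may be captured. Reconcile the two and apply one standard to both arms, since first detection depends on it.
- **Episode rate.** Keep it as secondary, with a prespecified rule for both arms covering the start, the end, the separating interval and AF seen by more than one method. State that it still depends on sampling frequency and on treatment after detection. Even a rule that ends an episode at an intervening sinus recording will split AF more often where recordings are more frequent.

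**Cost.** Endpoint and analysis wording only, with no new data. Repeat recurrences move to a secondary analysis. No stated power calculation is undone. Assuming two-sided 5% significance and 80% power, 150 per arm would detect 30% against 45.7% of participants with a detected recurrence.
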